8.1.2. Classification of Adverse Events

All AEs will be evaluated according to the NCI CTCAE v5.0 (effective 27 November 2017). If the AE is not listed in the CTCAE v5.0, it should be graded based on the description given in [Table 9](#).

Table 9: Adverse Event Severity

Severity	Definition
Grade 1 (Mild)	No limitation of usual activities.
Grade 2 (Moderate)	Some limitation of usual activities.
Grade 3 (Severe)	Inability to carry out usual activities.
Grade 4 (Life-threatening)	Immediate risk of death.
Grade 5 (Fatal)	Resulting in death.

Relationship of an AE or SAE to study medication is to be determined by the Investigator based on the definitions in [Table 10](#).

Table 10: Adverse Event Causal Relatedness

Relationship to Product(s)	Definition
Not Related	No relationship between the event, including laboratory test abnormality, and the administration of study drug. There is no temporal relationship and there is unambiguous evidence supporting another cause.
Unlikely Related	A clinical event, including laboratory test abnormality, with a temporal relationship to study drug administration which makes a causal relationship improbable, and in which other drugs, chemicals or underlying disease provide plausible explanations.
Possibly Related	A clinical event, including laboratory test abnormality, with a reasonable time sequence to administration of study drug, but which could also be explained by concurrent disease or other drugs or chemicals. Information on study drug withdrawal may be lacking or unclear.
Probably Related	A clinical event, including laboratory test abnormality, with a reasonable time sequence to administration of study drug, unlikely to be attributed to concurrent disease or other drugs or chemicals, and which follows a clinically reasonable response on withdrawal of study drug. The association of the clinical event, including laboratory test abnormality, must also have some biologic plausibility, at least on theoretical grounds.
Definitely Related	A clinical event, including laboratory test abnormality occurring in a plausible time relationship to study drug administration, and which cannot be explained by concurrent disease or other drugs or chemicals. The response to withdrawal of the study drug should be clinically plausible. The event must be definitive pharmacologically or phenomenologically, using a satisfactory re-challenge procedure if necessary.

Document ID: CLIN-00067	Title: IMGN853-0419 Clinical Study Protocol	Version: 2.0
Legacy ID: 26587		Approved Date: 12/22/202

8.2. Adverse Events

8.2.1. Reporting Serious Adverse Events

Any SAE, regardless of relationship to study medication, which occurs in a patient from the time of study informed consent until 30 days after the last study treatment, must be recorded by the clinical site on an SAE report form. Only SAEs which are considered related to a study procedure (ie, blood draw or fresh tumor biopsy) will be captured during the pre-screening period, ie, from the time of signing the pre-screening consent (if one is utilized) until the signing of the main study informed consent, or until the patient is determined to be a screen failure. The SAE must also be recorded in the clinical trial database, including the Investigator's assessment regarding the relationship of the SAE to the study drug. The Investigator will promptly supply all information requested by the Sponsor (or contract research organization [CRO]) regarding the SAE.

The Investigator must submit the SAE Report Form to ImmunoGen Pharmacovigilance (or designee). This form must be completed and submitted within 24 hours of the Investigator's learning of the event using the contact information printed on the SAE form and contained within the SAE form completion instructions. Follow-up information must also be submitted using a new SAE Report Form.

When reporting SAEs, the following additional points should be noted:

- The underlying diagnosis or syndrome should be reported as the primary SAE term, rather than the signs or symptoms (signs and symptoms may be described in the narrative).
- An event term of "Death" should not be reported as an SAE, but rather be recorded as an outcome of a specific SAE term. Initially, the event term of "death" can be used until the actual cause of death is known. If an autopsy was performed, the autopsy report should be provided.

It is the responsibility of the Sponsor to ensure that each Investigator receives a copy of any suspected unexpected serious adverse reaction (SUSAR) report (CIOMS/MedWatch) regarding the study drug and that the report is submitted to the appropriate national regulatory agencies.

The Investigator (or Sponsor or contracted designee) must promptly report all SUSARs to the IRB/IEC for review in accordance with their local IRB/EC requirements and national regulations. IRB/IEC notification of the SUSAR may take the form of a submission of a copy of the CIOMS/MedWatch report or other format accepted by the IRB/IEC. A copy of the CIOMS/MedWatch report and notification to IRB/IEC should be retained in the site's study files.

In addition to CIOMS/MedWatch reports, the Sponsor will also notify (through annual updates to the Investigator Brochure) the Investigators and IRBs/IECs of all deaths that occur during the study, irrespective of relationship to study medication.

Document ID: CLIN-00067	Title: IMGN853-0419 Clinical Study Protocol	Version: 2.0
Legacy ID: 26587		Approved Date: 12/22/202

8.2.1.1. Reporting of Disease Progression

Progressive disease (PD) is an anticipated occurrence in oncology drug development and is not an AE unto itself.

Progression of disease should not be reported as an SAE term; any serious medical event/condition that results from progression of underlying disease, if untoward, should be reported as the SAE.

Progression of disease with a fatal outcome does not need to be reported as an AE term. The applicable protocol CRF page(s) pertaining to death should be appropriately completed however, as PD.

8.2.2. Reporting a Pregnancy

Pregnancy and lactation are exclusion criteria. Women of child bearing potential, defined as a sexually mature woman who has not undergone surgical sterilization or who has not been naturally postmenopausal for at least 12 consecutive months (ie, who has had menses any time in the preceding 12 consecutive months) must agree to use highly effective contraceptive methods (as defined in [Section 5.8.7](#)) while on study drug and for at least 3 months after the last dose of MIRV. In addition, it is recommended that patients undergo monthly pregnancy test for at least 3 months after the last dose of MIRV.

The Sponsor must be immediately notified in the event of a pregnancy occurring during the study and through 30 days after a patient's last dose of MIRV. If a patient becomes pregnant the patient will be withdrawn from study drug. Pregnancy is not an AE unto itself and therefore should not be reported as an AE.

All pregnancies will be recorded on a Pregnancy report form and submitted according to the contact information on the form and in the completion guidelines.

Pregnancies, with the permission of the mother, will be followed to completion or termination using the designated sections of the Pregnancy report form.

Any SAE, occurring during the pregnancy to the mother or fetus, would require that a study SAE form also be completed/submitted.

9. STUDY ACTIVITIES

All study visits and assessments that must be performed during the study and follow-up are included in [Table 2](#).

9.1. Screening Visit

The Investigator is responsible for keeping a record of all patients screened for entry into the study, including those who are subsequently excluded. The reason(s) for exclusion must be recorded.

Document ID: CLIN-00067	Title: IMGN853-0419 Clinical Study Protocol	Version: 2.0
Legacy ID: 26587		Approved Date: 12/22/202

9.1.1. Standard of Care Assessments

In some cases, clinical assessments performed before obtaining informed consent may be used to qualify the patient for the study if performed within the screening window. These include radiologic tumor assessment, PEs, laboratory results, urinalysis, or other assessments which may be considered part of standard of care. In these cases, repeat assessments may not be necessary before enrollment, unless individual parameters require further study or confirmation and are clinically appropriate.

Note that safety blood tests, and PE do not need to be repeated if normal and conducted within 4 days prior to C1D1.

9.2. End of Treatment Visit

Patients may voluntarily withdraw from the study drug at any time for any reason, and without prejudice to further treatment. In addition, patients may be withdrawn by the Investigator if they do not feel the patient is deriving clinical benefit or because the patient is experiencing unacceptable toxicity. The reasons for which a patient may be prematurely discontinued are listed in [Section 5.6](#). The clinical trial database will capture reasons for withdrawal.

Patients who withdraw or are removed from the study treatment will have an EOT visit within 7 days of the decision to discontinue study drug. Patients will undergo assessments as outlined in [Table 2](#).

9.3. Follow-up Assessments

9.3.1. 30-Day Follow-up Visit

A 30-Day Follow-up visit will occur 30 days (+14 days) after last dose of MIRV and should occur prior to the start of new anticancer therapy.

In some cases, nonserious AE observations may continue beyond the safety visit. All ocular AEs will be followed until resolution, stabilization, or return to baseline. In these instances, additional information may be requested by ImmunoGen to adequately categorize the nature of the toxicity.

All SAEs will be followed until they resolve, stabilize, or return to baseline, regardless of time from last dose or last visit.

9.3.2. Response Follow-up

Patients who discontinued MIRV for reasons other than PD will continue with tumor assessments until documentation of PD or the start of a new anticancer therapy, whichever comes first. Prior to Week 36 (from C1D1), assessments should occur every 6 weeks (\pm 1 week) as allowed by local requirements but must occur at an interval of no more than 12 weeks. After Week 36, assessment will occur every 12 weeks (\pm 3 weeks) until documentation of PD or the start of new anticancer therapy.

Document ID: CLIN-00067	Title: IMGN853-0419 Clinical Study Protocol	Version: 2.0
Legacy ID: 26587		Approved Date: 12/22/202

9.3.3. Survival Follow-up

All patients who discontinue MIRV for any reason will be followed for survival after PD as per Investigator, or after start of a new anticancer therapy. Survival status will be assessed every 3 months (\pm 1 month) until death, lost to follow-up, withdrawal of consent for survival follow-up, or until EOS, whichever comes first. Additional survival follow-up calls may occur periodically if needed.

10. STATISTICAL METHODS

This is a Phase 2 study designed to evaluate the ORR of MIRV in patients with high FR α expressing, high-grade serous rPSOC.

All patients who have received at least 1 dose of MIRV will comprise the Safety Analysis Population.

The Efficacy Evaluable Population will include all patients who have received at least 1 dose of MIRV and have measurable lesions at baseline (per RECIST v1.1). The primary efficacy analysis of ORR and all other efficacy analyses will be based on the Efficacy Evaluable Population.

The safety analyses will be based on Safety Analysis Population.

All statistical analyses will be performed using SAS statistical software Version 9.4 or later, unless otherwise noted. For categorical variables, the number (n) and percent of each category within a parameter will be presented. For continuous variables, the sample size (n), mean, median, and standard deviation, as well as the minimum and maximum values, will be presented. Missing data will not be imputed unless otherwise stated. There will be a detailed description of patient disposition, patient demographics, and baseline characteristics.

A SAP will fully describe the planned analyses for this trial and will be finalized prior to database lock.

10.1. Sample Size

The primary endpoint of this study is ORR as assessed by the Investigator. The study is designed to test the null hypothesis that the ORR is \leq 28% using an optimal Simon's two-stage design ([Simon 1989](#)) without a planned pause in enrollment given preliminary efficacy and established safety of MIRV.

The optimal two-stage design to test the null hypothesis that the ORR is \leq 28% versus the alternative that the ORR is \geq 48%, has an expected sample size of 37.74, and a probability of early termination of 0.762. If the ORR is \leq 28%, there is a 0.024 probability of rejecting the null hypothesis (the target 1 sided alpha value was 0.025). If the ORR is \geq 48%, there is a 0.9 probability of rejecting the null hypothesis. After testing the drug on 28 efficacy evaluable patients in the first stage, the study will be terminated for futility if 9 or fewer patients respond. If the study goes on to the second stage, a total of 69 efficacy evaluable patients will be enrolled. If the total number responding is more than 26, the null hypothesis is rejected.

Document ID: CLIN-00067	Title: IMGN853-0419 Clinical Study Protocol	Version: 2.0
Legacy ID: 26587		Approved Date: 12/22/202

Approximately 75 patients will be enrolled so that a total of 69 patients will be efficacy evaluable.

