3. STUDY POPULATION

3.1. Criteria for Selection of Patient Population

3.1.1. Inclusion Criteria

1. Patients \geq 18 years of age
2. Patients must have an Eastern Cooperative Oncology Group Performance Status (ECOG PS) of 0 or 1
3. Patients must have a confirmed diagnosis of high-grade serous EOC, primary peritoneal cancer, or fallopian tube cancer
4. Patients must have platinum-sensitive disease defined as radiographic progression greater than 6 months from last dose of most recent platinum therapy

Note: Progression should be calculated from the date of the last administered dose of platinum therapy to the date of the radiographic imaging showing progression

5. Patients must have progressed radiographically on or after their most recent line of anticancer therapy
6. Patients must have at least 1 lesion that meets the definition of measurable disease by Response Evaluation Criteria in Solid Tumors version 1.1 (RECIST v1.1) (radiologically measured by the Investigator)
7. Patients must be willing to provide an archival tumor tissue block or slides, or undergo procedure to obtain a new biopsy using a low-risk, medically routine procedure for immunohistochemistry (IHC) confirmation of FR α positivity
8. Patient's tumor must be positive for FR α expression as defined by the Ventana FOLR1 Assay
9. Prior anticancer therapy

- a. Patients must have received at least 2 prior systemic lines of platinum therapy and be considered by the Investigator as appropriate for single-agent non-platinum therapy (documentation required – eg, high risk of hypersensitivity reaction; risk of further cumulative toxicity with additional platinum, including but not limited to myelosuppression, neuropathy, renal insufficiency or other)

Note: Patients who have had a documented platinum allergy may have had only 1 prior line of platinum

- b. Patients may have received up to but no more than 1 prior independent non-platinum cytotoxic therapy
- c. Patients must have had testing for *BRCA* mutation (tumor or germline) and, if positive, must have received a prior PARP inhibitor as either treatment or maintenance therapy
- d. Neoadjuvant \pm adjuvant therapies are considered 1 line of therapy
- e. Maintenance therapy (eg, bevacizumab, PARP inhibitors) will be considered part of the preceding line of therapy (ie, not counted independently)

Document ID: CLIN-00067	Title: IMGN853-0419 Clinical Study Protocol	Version: 2.0
Legacy ID: 26587		Approved Date: 12/22/202

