14. Patients who received prior treatment with MIRV or other FR α -targeting agents
15. Patients with untreated or symptomatic central nervous system (CNS) metastases
16. Patients with a history of other malignancy within 3 years prior to enrollment

Note: patients with tumors with a negligible risk for metastasis or death (eg, adequately controlled basal-cell carcinoma or squamous-cell carcinoma of the skin, or carcinoma in situ of the cervix or breast) are eligible.
17. Prior known hypersensitivity reactions to study drugs and/or any of their excipients

Prospective approval of protocol deviations to recruitment and enrollment criteria, also known as protocol waivers or exemptions, is not permitted.

Document ID: CLIN-00067	Title: IMGN853-0419 Clinical Study Protocol	Version: 2.0
Legacy ID: 26587		Approved Date: 12/22/202

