5.2.1. Enrolled Patient Definition

Patients who have consented to the study and have received at least 1 dose of study drug, are considered enrolled. Patients who are issued a patient number, but who do not successfully complete the screening process and are not treated will be considered screen failures. Patient numbers for patients who screen fail will not be re-issued.

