6.1.1.1. ORR

The ORR will be calculated as the number of patients with a confirmed BOR of CR or PR divided by the number of patients in the Efficacy Evaluable population. Patients without at least 1 post-baseline RECIST assessment will be treated as non-responders (i.e., these patients will contribute to the denominator, but not the numerator).

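### The plan's definitions leave almost no route from 75 enrolled to 69 evaluable; at 75 the fixed count of 27 responders has type I error 0.056 and conflicts with the SAP's confidence-interval rule

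*Protocol*

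**What the plan says.** **Sample size.** Protocol 10.1: "The study is designed to test the null hypothesis that the ORR is \leq 28% using an optimal Simon's two-stage design", "versus the alternative that the ORR is \geq 48"%. The first stage has 28 efficacy evaluable patients and stops for futility at 9 or fewer responders. The total is 69 evaluable, and "If the total number responding is more than 26, the null hypothesis is rejected". The stated type I error is 0.024 (one-sided target 0.025) and the stated power 0.9. The enrolment figure follows: "Approximately 75 patients will be enrolled so that a total of 69 patients will be efficacy evaluable". SAP 3.2.2 repeats all of this.

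**Who is enrolled.** Protocol 5.2.1: "Patients who have consented to the study and have received at least 1 dose of study drug, are considered enrolled". Patients not treated are screen failures.

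**Who is evaluable.** Protocol section 10 requires at least one dose and measurable lesions at baseline. SAP 4.12.3 makes this measurability per Investigator for the Investigator-assessed endpoints.

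**Eligibility.** Inclusion criterion 6 (Protocol 3.1.1): "Patients must have at least 1 lesion that meets the definition of measurable disease by Response Evaluation Criteria in Solid Tumors version 1.1", and it names the Investigator as the one who measures it. Protocol 3.1.2 ends: "Prospective approval of protocol deviations to recruitment and enrollment criteria, also known as protocol waivers or exemptions, is not permitted".

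**Denominator.** SAP 6.1.1.1: "Patients without at least 1 post-baseline RECIST assessment will be treated as non-responders".

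**A second decision rule.** SAP 4.10 rejects the null if the lower limit of the two-sided 95% Clopper-Pearson interval exceeds 28%, and SAP 4.11.1 confirms that testing is by confidence interval. SAP section 9, which lists departures from the protocol, mentions only the timing of the ORR analysis.

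**The concern.** Going from 75 to 69 assumes that 6 of 75 patients (8%) will be dosed but not evaluable. The usual sources of such a loss are closed off. Dropout before dosing is screen failure, not enrolment. A missing follow-up scan keeps the patient in the denominator as a non-responder. Lack of a measurable lesion bars entry, judged by the same reader who defines the primary analysis population. The BICR-evaluable population can be smaller, but it serves only a sensitivity analysis.

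The primary analysis uses the whole Efficacy Evaluable population, and neither document limits the test to the first 69 or says how the count changes for another total. At the planned enrolment, therefore, the number analysed will probably not be the number for which the count, the 0.024 and the 0.9 were derived. At stake is the pass mark for the primary endpoint: for some attainable results the documents give both a rejection and a non-rejection.

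**Working it through.** **Inputs** (Protocol 10.1): null ORR 0.28; alternative 0.48; first stage n1 = 28, stop if 9 or fewer respond; reject if 27 or more respond in total; design N = 69; planned enrolment 75.

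**Formula.** With X1 ~ Bin(28, p) and X2 ~ Bin(N − 28, p),

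P(reject) = Σ over x = 10 to 28 of P(X1 = x) · P(X2 > 26 − x).

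**Plan's own figures, N = 69.** Type I error 0.0245 (stated 0.024), power 0.9001 (0.9), probability of early termination P(X1 ≤ 9) = 0.7624 (0.762). Expected N = 28 + 41 × (1 − 0.7624) = 37.74 (37.74). The published design reproduces.

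**Implied loss.** 1 − 69/75 = 0.08, that is, 6 patients.

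**Same count, other evaluable totals, futility stop kept:**

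| Evaluable N | Non-evaluable of 75 | Type I error | Power |
|---|---|---|---|
| 69 | 6 | 0.024 | 0.900 |
| 70 | 5 | 0.029 | 0.908 |
| 71 | 4 | 0.033 | 0.914 |
| 72 | 3 | 0.039 | 0.918 |
| 73 | 2 | 0.044 | 0.922 |
| 74 | 1 | 0.050 | 0.925 |
| 75 | 0 | 0.056 | 0.927 |

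The count passes the 0.025 target from N = 70. If the futility bound is not followed, the single-stage tail P(Bin(75, 0.28) ≥ 27) is 0.081.

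**SAP 4.10 rule.** The Clopper-Pearson lower limit for x of N is the 0.025 quantile of Beta(x, N − x + 1).

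| Result | Observed ORR | Lower limit | Count rule | SAP 4.10 |
|---|---|---|---|---|
| 27/69 | 39.1% | 27.6% | reject | do not reject |
| 28/69 | 40.6% | 28.9% | reject | reject |
| 27/75 | 36.0% | 25.2% | reject | do not reject |
| 28/75 | 37.3% | 26.4% | reject | do not reject |
| 29/75 | 38.7% | 27.6% | reject | do not reject |
| 30/75 | 40.0% | 28.9% | reject | reject |

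Putting the SAP 4.10 thresholds into the two-stage formula gives:
- N = 69, 28 or more responders: type I error 0.014, power 0.875.
- N = 75, 30 or more responders: type I error 0.014 (0.017 without futility stopping), power 0.890.

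The stated pair of 0.024 and 0.9 therefore describes the count rule at 69. It does not describe either rule at 75.

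**The case against.** The strongest objection is that the SAP already contains a rule that adapts to the number analysed. Protocol section 10 leaves the full description of the analyses to the SAP, and SAP 4.10 and 4.11.1 test by the Clopper-Pearson interval. Under that rule the type I error stays below 0.025 at every evaluable total from 69 to 79, with or without futility stopping. This stands. A reader might infer that the trial as planned runs at a 5.6% error rate and would declare success at 27 of 75. The documents do not support that: 27 of 75 has a lower limit of 25.2%, and SAP 4.10 would not reject.

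Second, the count sits directly after the sentence fixing 69 evaluable patients, and nothing tells the analyst to carry it over to 75. This also stands. The text leaves a gap; it does not instruct anyone to use the count at 75.

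Third, a reader might infer that every enrolled patient must be evaluable. That is too strong. Protocol 5.6.1 foresees erroneous inclusion, SAP 4.12.5 foresees eligibility deviations among dosed patients, and SAP 5.1 provides for more than 5% of the Safety population falling outside the evaluable population. But no rate is given, and reaching 69 would take six errors on one criterion.

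These points do not close the matter. SAP 3.2.2 restates the count as a rejection rule in the same document as 4.10, SAP section 9 does not withdraw it, and the protocol contains no other rejection rule.

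**Conclusion.** The point holds as an inconsistency in the primary decision rule, not as a demonstrated inflation of the trial's error rate. By the plan's definitions, enrolling about 75 should yield close to 75 evaluable patients, and the allowance of 6 is unexplained.

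If the count governs and the futility stop is followed, the type I error lies between 0.024 and 0.056 for an assumed 6 down to 0 non-evaluable patients of 75. If SAP 4.10 governs, the error is controlled at 0.014 with 75 evaluable, and power is 0.890 instead of the stated 0.9. The rules already disagree at 27 of 69; enrolling to 75 widens the disagreement from one responder count to three (27, 28 and 29).

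The operating characteristics are exact binomial results. The number of eligibility errors is an assumption, because the documents give none.

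**What to change.** In Protocol 10.1 and SAP 3.2.2, either justify the 75-to-69 allowance or say that essentially all enrolled patients are expected to be evaluable. Then state one governing rule, in one of two ways:

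- **(a)** Make the Clopper-Pearson criterion of SAP 4.10 the only rejection rule, applied to the evaluable number actually treated, and remove the count of 27 as a rejection rule. Quote the matching figures: for 75 evaluable, 30 responders, type I error 0.014, power 0.890.
- **(b)** Keep the Simon count, apply it to the first 69 evaluable patients by date of first dose, report all evaluable patients as the supporting estimate, and amend SAP 4.10 to match. The stated 0.024 and 0.9 then apply, provided the futility stop is followed; without it the type I error at 69 is 0.030.

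Recalibrating the count alone is not enough. At 75, a cutoff of 29 or more has type I error 0.0235 and power 0.909, but 29 of 75 has a lower limit of 27.6% and would still fail SAP 4.10.

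The cost is wording in the two documents, with no extra patients. Under (a), stated power falls slightly below 0.90. Under (b), patients beyond the 69th do not enter the formal test.
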